**Causal Lesion Network Guided Treatment of Bipolar Mania
With Transcranial Electrical Stimulation**

NCT #: NCT05445466

June 23, 2025

Protocol Number:	2022P000295
Title:	Causal Lesion Network Guided Treatment of Bipolar Mania With Transcranial Electrical Stimulation
Design:	Double blind, design with baseline, day 5, 1 month and 3 month follow up visits during which transcranial electrical stimulation (tES) was delivered to the right orbital frontal cortex (rOFC) from baseline to day 5 each day (5 days) twice a day for 20 mins. Participants were randomly assigned to either cathodal transcranial direct current (tDCS), 10hz or personalized transcranial alternating current (tACS) conditions to test the effectiveness and feasibility of stimulating the rOFC using a novel targeting methodology consisting of a lesion network guided brain target linked to mania symptoms.
Objectives:	Evaluate the effectiveness and safety of transcranial electrical stimulation for improving the mania symptoms
Enrollment:	14 Individuals
Clinical Sites:	Beth Israel Deaconess Medical Center, Boston, MA
Patient Population:	Male or female outpatients 18-65 years of age patient's diagnosis with either bipolar or schizoaffective disorder, or history of mania as defined by DSM-5 or DSM-IV-TR criteria
Primary and Secondary Outcomes:	Primary Outcomes: Young Mania Rating Scale (YMRS); Altman Self-Rated Mania Scale (ASRM); Average Hospitalizations Secondary Outcomes: Balloon Analogue Risk Task (BART); The Go/No Go Task; Reinforcement Learning Task (RLT); Social Functioning Scale (SFS); Positive and Negative Syndrome Scale (PANSS); Global Assessment of Functioning (GAF); Barret Impulsiveness Scale (BIS); Resting State EEG; Brief Assessment of Cognition (BAC); Montgomery-Asberg Depression Rating Scale (MADRS)
Inclusion Criteria:	
 1. Aged 18-65 years of age 2. Proficient in English 3. Able to give informed consent 4. Meet diagnostic criteria for bipolar disorder or schizoaffective disorder, bipolar type as verified by the SCID 5. History of mania (>1 lifetime episode) 6. Experiencing mild to moderate symptoms of mania 7. No changes to mood stabilizing medications for a period of 2 weeks prior to participation 8. Has not recently participated in tES/TMS treatments

	In addition to the criteria above, participants for this stimulation procedure will be included if they have a history of mania and may or may not be experiencing symptoms currently.

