Exclusion Criteria:	
 1. Substance abuse or dependence (w/in past 6 months) 2. Those who are pregnant/breastfeeding 3. History of head injury with > 15 minutes of loss of consciousness/mal sequelae 4. DSM-V intellectual disability 5. Having a non-removable ferromagnetic metal within the body (particularly in the head) 6. History of seizures
Statistical Methodology:	Within and between comparisons to statistically detect differences in symptoms, tasks and electrophysiology measures before and after treatment conditions (cathodal tDCS, 10hz and personalized tACS). To determine the effectiveness and feasibility of targeting the rOFC with a novel targeting methodology to engage target outcomes.

Statement: The design, conduct and reporting of this trial shall be conducted in accordance with the protocol, the United States 45 Code of Federal Regulations (CFR) part 46 known as “The Common Rule”, 45 CFR 164.502(d), and 164.514(a)-(c) known as “The Privacy Rule” of the Health Insurance Portability and Accountability Act (HIPAA), and the International Conference on Harmonization (ICH)/Good Clinical Practice (GCP). All Investigators will have documented training in The Collaborative Institutional Training Initiative (CITI Program) in Biomedical Research and GCP.

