Description of Study Endpoints

Primary Endpoint

Change from baseline to day 5, 1 month and 3 month in clinical measures (PANSS, ASRM) and hospitalizations after 1 week of tES.

Secondary Endpoints

Change from baseline to day 5, 1 month and 3 month in GAF, SFS total score after 1 week of tES. Change from baseline to day 5 and 1 month in MADRS, PANSS, BIS after 1 week of tES. Change from baseline to day 5 and 1 month in voltage and peak frequency for reinforcement learning task measures after 1 week of tES. Change from baseline to day 5, 1 month and 3 month in cognition scores after 1 week of tES. Change from baseline to day 5, 1 month and 3 month in behavioral tasks (BART & Go/No Go) scores after 1 week of tES.

Safety and Tolerability Endpoint

A self-rated questionnaire related to sensations of tES is given to participants after each stimulation.

General Statistical Considerations

All collected study data will be collected on Redcap and processed using R and Matlab software. Descriptive statistics (n, mean, standard deviation, median, minimum and maximum) will be calculated by treatment group and sham group for continuous variables.

Primary Analyses

Primary Analysis of the primary, secondary, and additional efficacy endpoints: Mixed Model Repeated Measures analysis (MMRM)/non- parametric methods will be used to compare using within group differences as well as to determine the difference between the two treatment groups on the primary, secondary and safety endpoints depending on the distribution of the data.

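### Within-group change is tested as a primary efficacy analysis beside the randomised between-group comparison, with no statement of which governs and no operational rule for choosing the test

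*Combined protocol and SAP*

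**What the plan says.** The Primary Analyses section is one sentence, introduced as the "Primary Analysis of the primary, secondary, and additional efficacy endpoints". It says that MMRM or "non- parametric methods will be used to compare using within group differences" and, in the same clause, that these methods will "determine the difference between the two treatment groups". The method is to be chosen for the primary, secondary and "safety endpoints depending on the distribution of the data". No non-parametric test, sidedness, normality check, cut-off or time of decision is given.

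The synopsis (Statistical Methodology) gives both comparisons the same standing: "Within and between comparisons to statistically detect differences in symptoms, tasks and electrophysiology measures before and after treatment conditions". The Primary Objective is the effectiveness of transcranial electrical stimulation (tES) on mania symptoms and names no comparator. The Study Rationale asks a comparative question: personalized tACS against tDCS or sham.

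Three further items bear on the point:

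- **Size.** Enrollment is "14 Individuals". No allocation ratio is stated.
- **Groups.** The synopsis randomises three active conditions (cathodal tDCS, 10 Hz tACS, personalized tACS). Primary Analyses speaks of two treatment groups. General Statistical Considerations says that descriptive statistics "will be calculated by treatment group and sham group for continuous variables".
- **Primary scale.** The synopsis and the Primary Objective name YMRS and ASRM, with hospitalizations. The Primary Endpoint reads "Change from baseline to day 5, 1 month and 3 month in clinical measures" and then names PANSS and ASRM, with hospitalizations.

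**The concern.** A before-after test within one condition asks whether scores changed. It does not ask whether stimulation changed them. Natural course, repeated rating, expectation and, depending on who is enrolled, regression to the mean all enter the result. The trial has the remedy, because it randomises concurrent conditions, but the plan does not say that the randomised comparison decides the conclusion. Followed as written, it allows a before-after p-value in one condition to be reported as a primary efficacy result.

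It also invites the report that one condition was significant and another was not. With four or five people per condition that pattern arises often by chance when the conditions are equally effective or equally ineffective.

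The method-choice rule is a lesser part of the concern. It leaves open which analysis is the planned one, for the within-group and the between-group comparison alike.

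**Working it through.** The plan gives no alpha, power, effect size or SD, so there is no stated figure to reproduce. The calculations below show how the two kinds of comparison behave at this size.

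**Inputs.** From the documents: 14 participants and three conditions (or two groups, on the Primary Analyses wording). Assumed: two-sided alpha 0.05, normal data, variance pooled across conditions, one scale at one visit, no dropout, and a split of 5/5/4 or 7/7.

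**Step 1: one within-condition test.** With true mean change d in SDs of the change score, the test statistic is noncentral t with noncentrality d√n and 14 − 3 = 11 df. At d = 0.5, 1.0 and 1.5 the chance of significance is 18%, 53% and 86% for n = 5, and 15%, 45% and 78% for n = 4.

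**Step 2: all conditions together, same true change in each.** Treating the three tests as independent at d = 1.0:

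- P(none significant) = 0.468² × 0.554 = 0.121
- P(all significant) = 0.532² × 0.446 = 0.126
- P(some but not all) = 1 − 0.121 − 0.126 = 0.753

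The shared variance estimate makes the tests positively dependent. Simulation that allows for this (400,000 trials per row) gives:

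| Common true change | Some but not all significant, 5/5/4 | At least one significant, 5/5/4 | Some but not all significant, 7/7 | Direct between-condition test |
|---|---|---|---|---|
| 0.5 SD | 38% | 40% | 32% | 5% |
| 1.0 SD | 67% | 84% | 39% | 5% |
| 1.5 SD | 38% | 99% | 8.5% | 5% |

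No condition differs from another in any row. The change is real, but nothing in a within-condition test ties it to stimulation.

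**Step 3: regression to the mean.** With no effect, retest correlation ρ and entry restricted to a band of baseline scores, the expected fall is (1 − ρ) × the band's mean, measured in SDs above the population mean. For a band of 0.5 to 1.5 SD, mean 0.92, and ρ = 0.5, this is 0.5 × 0.92 = 0.46 SD. The rate of falsely significant improvement in an arm of 5 (paired t with the arm's own variance, nominal 2.5% in that direction), for ρ = 0.5 and 0.7, is:

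- No selection: 2.5% at both
- Band centred on the mean (−0.5 to 0.5 SD): 2.5% at both
- Band below the mean (−1 to 0 SD): about 1% at both
- Band 0 to 1 SD: 7% and 5%
- Band 0.5 to 1.5 SD: 15% and 10%

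The inclusion criteria ask for mild to moderate current mania, but a note below them admits people with or without current symptoms. The documents therefore do not settle which line applies.

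**Step 4: what the randomised contrast can detect.** A baseline-adjusted model leaves 14 − 3 − 1 = 10 error df. At 5 v 5 the standard error is √(1/5 + 1/5) = 0.632 adjusted SD (the SD after adjusting for baseline). The 95% CI half-width is 2.228 × 0.632 = 1.41 adjusted SD. The difference detectable with 80% power (noncentral t) is 1.97 adjusted SD, or 2.09 at 5 v 4.

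**The case against.** The strongest reply is that the between-group comparison is planned, in the same sentence, and that nothing says p-values will be compared across conditions. That is right as far as it goes. A reader might infer that the trial has no concurrent comparator. The documents do not support this: the lack of a comparator is a property of the within-group test only. What remains is that the two comparisons are unranked under a primary heading, while the stated objective names no comparator.

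A second reply is that a basis for choosing the method is given. It is: the distribution of the data. What is missing is an operational rule. Three stronger readings are tempting here.

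- **That the test would be picked after unblinding.** The plan gives no timing, and a blinded look at pooled data fits the text.
- **That switching tests inflates the between-condition error.** A check that switched between the F test and Kruskal-Wallis on an assumed Shapiro-Wilk test gave 4.5% to 5.1%, which is no inflation.
- **That the non-parametric branch could never reach significance.** An exact two-sided signed-rank test has a smallest p of 2/2⁵ = 0.0625 at n = 5. But the plan names no test, and the floor is gone with six or more in an arm or with two groups of 7.

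On regression to the mean, it is fair to say that inflation needs selection of above-average scores, which is not established.

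Finally, this is a 14-person study. That argues for estimation, but it does not rescue the within-group test, because the stated aim is effectiveness.

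**Conclusion.** The point holds as a defect in which analysis governs, with the method-choice rule as a secondary gap. At 5/5/4, and with equal true change of 0.5 to 1.5 SD in every condition, a split verdict across conditions appears in about 38% to 67% of trials. At least one condition is significant in about 40% to 99%. The direct between-condition test stays at 5%. With two groups of 7 the split verdict is less common, at about 9% to 39%. Regression to the mean adds anything from nothing to a rate of about 15% against 2.5% nominal in an arm of 5, depending on entry selection that the documents leave open.

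These sizes rest on the assumed alpha, normality, pooled variance (the arm's own variance for regression to the mean), single scale and visit, no dropout, and the assumed splits. The gap in ranking rests on the text alone. It should be corrected. It does not show that the planned between-group test is invalid.

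**What to change.** 1. State that the randomised between-condition comparison governs the efficacy conclusion. Report within-condition change as mean and 95% CI, labelled as having no comparator, with no p-value and no efficacy claim.
2. First reconcile the primary mania scale (YMRS and ASRM in the synopsis and Primary Objective; PANSS and ASRM in the Primary Endpoint). Reconcile the groups too: three active conditions in the synopsis, two treatment groups and a sham group in the statistical sections, tDCS or sham in the Study Rationale.
3. For the reconciled scale at one named visit, fix one baseline-adjusted MMRM in advance. The sponsor should name one contrast or use the overall test of condition. Use a permutation test that follows the actual randomisation as the sensitivity check.
4. Remove the clause on the distribution of the data for this primary scale analysis only. Name in advance a suitable method for hospitalizations (counts) and for the 0–4 sensation ratings, which the MMRM on the mania scale does not cover.
5. If there is no sham arm, state that only relative effects between active conditions can be concluded.
6. The synopsis describes assignment in the past tense. If outcome data have been seen, label the change post hoc.

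The cost is SAP wording and a little programming. Within-group significance claims are given up, and the remaining contrast is weak: about 2.0 adjusted SD detectable with 80% power at 5 v 5 without dropout. Results should therefore be presented as estimates with CIs.

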Background: Mania is a core symptom of bipolar disorder involving periods of euphoria. Decreased inhibitory control, increased risk-taking behaviors, and aberrant reward processing are some of the more recognized symptoms of bipolar disorder and are included in the diagnostic criteria for mania. Current drug therapies for mania are frequently intolerable, ineffective, and carry significant risk for side effects. Presently there are no neurobiologically informed therapies that treat or prevent mania. However, using a newly validated technique termed lesion network mapping, researchers demonstrated that focal brain lesions having a causal role in the development of mania in people without a psychiatric history can occur in different brain locations, such as the right orbitofrontal cortex (OFC), right dorsolateral prefrontal cortex (DLPFC), and right inferior temporal gyrus (ITG). This lesion network evidence converges with existing cross-sectional and longitudinal observations in bipolar mania that have identified specific disruptions in network communication between the amygdala and ventrolateral prefrontal cortex. The OFC is associated with inhibitory control, risk-taking behavior, and reward learning which are major components of bipolar mania. Thus, the association between

OFC with mania symptoms, inhibitory control, risk-taking behavior, and reward processing suggests that this region could be targeted using non-invasive brain stimulation.

Transcranial Electrical Stimulation (tES): tES is a non-invasive brain stimulation technique which modulates cortical excitability by a weak electrical current [< 4 milliamps (mA)] between two electrodes via direct current (DC), alternating current (AC), random noise (RN) or oscillatory current (OC). This study will utilize cathodal tDCS, 10hz and personalized tACS. Five days of twice a day (2x20min) of tES will be used during the week.

Electroencephalography (tES): EEG is a routine, non-invasive procedure to record brain activity. EEG electrodes will be attached to the skin indirectly. Most of the electrodes are mounted in an elastic cap, which is fitted over the head and held in place with elastic straps. Some additional electrodes are placed next to the eyes, on the forehead, or behind the ears, and are held in place with adhesive collars. Electrical contact between the skin and the electrodes is achieved via a water-soluble electrode gel.

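### The analysis compares two unnamed treatment groups and summarises a sham group, but the stated randomisation has three active conditions and no sham

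*Combined protocol and SAP*

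**What the plan says.** The arms are described in five places in the combined protocol and SAP, and the descriptions differ.

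- **Synopsis, Design:** "Participants were randomly assigned to either cathodal transcranial direct current (tDCS), 10hz or personalized transcranial alternating current (tACS) conditions". The same sentence describes visits "during which transcranial electrical stimulation (tES) was delivered to the right orbital frontal cortex (rOFC"), with no exception for a control arm. Enrollment is "14 Individuals", with no allocation ratio and no number per arm.
- **Synopsis, Statistical Methodology:** within and between comparisons "before and after treatment conditions (cathodal tDCS, 10hz and personalized tACS"). A stated purpose is "To determine the effectiveness and feasibility of targeting the rOFC with a novel targeting methodology to engage target outcomes".
- **Background, tES paragraph:** "This study will utilize cathodal tDCS, 10hz and personalized tACS".
- **Study Rationale:** the question is whether personalized stimulation does better than tDCS or a sham.
- **General Statistical Considerations and Primary Analyses:** descriptive statistics are split into treatment and sham. For every class of endpoint, safety included, the MMRM or a non-parametric method then "will be used to compare using within group differences as well as to determine the difference between the two treatment groups".

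The Primary Objective is the effectiveness of tES on mania symptoms. No section gives a pooling rule, a reference arm, a list of contrasts or a sham procedure.

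**The concern.** Primary Analyses is the only section that specifies a model, and it refers to a pair of groups that the design sections do not contain. The primary test could be any active pair, tDCS against pooled tACS, a comparison across three conditions, or treatment against sham. These answer different questions, and choosing among them after seeing data inflates the false-positive rate.

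What the trial can conclude is also at stake. Without a sham arm, between-group contrasts estimate only relative effects. Before-after change mixes any effect of tES with natural course, regression to the mean and placebo response. The three named conditions also share the rOFC target, so no contrast among them tests whether the targeting method works.

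**Working it through.** **1. Candidate arm sets against the text**

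| Arm set | Fits | Conflicts with |
|---|---|---|
| Three active arms | Synopsis, Background | Sham in Rationale and descriptive statistics; two groups in Primary Analyses |
| tDCS v pooled tACS | Two groups in Primary Analyses | Sham unexplained; pooling stated nowhere; tACS conditions listed separately |
| tDCS, personalized tACS, sham | Rationale, analysis sections | Omits the 10 Hz condition of the synopsis and Background |
| Three active arms plus sham | Sham wording | Two groups in Primary Analyses; no sham in the design sections |
| One treatment v sham | Descriptive statistics | Three conditions in the synopsis and Background |

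Each of these sets contradicts at least one section.

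**2. Plan's own figure.** The enrollment of 14 cannot be reproduced, because no alpha, power, effect size, SD or allocation is given. The figures below are illustrations under assumptions that are not in the documents: all 14 are randomised, one normal outcome at one visit, two-sided 5%, 80% power, and allocation 5/5/4 (three arms) or 4/4/3/3 (three active plus sham). The number randomised could be lower, because those who fail the toxicology screen are withdrawn.

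**3. False-positive rate if every reading is tried.** Simulation under no effect, using pooled-variance t-tests and counting any p<0.05. Ranges cover which arm is the smaller.

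| Readings tried | Rate |
|---|---|
| One named contrast | 5% |
| Three arms: 3 pairs | 12.3% |
| Three arms: 3 pairs plus tDCS v pooled tACS | 13.4-13.6% |
| Three arms: all 6 two-group splits | 15.8-15.9% |
| With sham: personalized v sham and pooled active v sham only | about 8% |
| With sham: each active arm v sham, and pooled active v sham (4) | about 14% |
| With sham: those 4 plus 3 active pairs and tDCS v pooled tACS (8) | 23-24% |

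These cover one outcome at one visit. Primary Endpoint lists 3 outcomes at 3 visits, so the candidate primary tests number 4 × 3 × 3 = 36 without sham, or 8 × 3 × 3 = 72 with it.

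**4. Detectable standardised difference.** Solve P(T > t₀.₉₇₅) = 0.80, where T is noncentral t with noncentrality δ; then d = δ × √(1/n₁ + 1/n₂).

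- Two-group t-test, 5 v 5: 8 df, t = 2.306, δ = 3.20, √(1/5 + 1/5) = 0.632, so d = 3.20 × 0.632 = 2.02.
- By the same method: 5 v 4, 2.19; 5 v 9, 1.70; 4 v 10, 1.81; 7 v 7 (one treatment v sham), 1.63.
- Baseline-adjusted, three arms: 14 − 3 − 1 = 10 df, δ = 3.11; a pair gives 1.97 (5 v 5) to 2.09 (5 v 4) residual SDs.
- Baseline-adjusted, four arms: 14 − 4 − 1 = 9 df, δ = 3.15; a pair gives 2.23 (4 v 4) to 2.57 (3 v 3), and pooled active v sham gives 1.86 (10 v 4) to 2.05 (11 v 3).

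**The case against.** The strongest reply is that the error may be confined to two phrases. The synopsis Statistical Methodology already plans comparisons across all three conditions, and an MMRM takes a three-level factor without a change of method. That is true of the model, but the statement names no contrast, so it does not say what the primary test is.

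A sixth reading is possible: 10 Hz tACS is the comparator loosely called sham, and the two treatment groups are cathodal tDCS and personalized tACS. This fits more of the text than the five sets tabulated. However, the documents never say so, the synopsis lists 10 Hz among the treatment conditions, and 10 Hz would not be an inert control.

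Three points stand. The documents do not settle whether a sham was randomised. The design sentence leans against it, but the no-sham consequences remain conditional. The false-positive figures assume an exhaustive search that nothing in the documents suggests, and the detectable differences concern sample size rather than the mismatch. The covariance structure and degrees-of-freedom method suggested below are sensible choices, but they do not follow from the contradiction.

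Blinding does not imply a sham, since active arms can be blinded to each other.

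**Conclusion.** The concern holds and must be fixed. The two-group rule does not match the stated randomisation, and no other section repairs it. Confidence is high for the mismatch, which rests on the text alone.

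If no sham was randomised, no between-group contrast addresses the Primary Objective, and the targeting claim is not tested either. If one was randomised, the design sections omit an arm. Either way, the reader cannot tell what the primary test compares.

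Under the stated assumptions, an exhaustive search would raise the 5% error rate to at most about 16% (three arms) or 24% (three active plus sham) for one outcome at one visit. Naming the contrast removes that freedom, but it does not make the trial well powered: even 7 v 7 detects only 1.63 SD.

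**What to change.** 1. Reconcile the synopsis, Background, Study Rationale and analysis sections. State the arms actually randomised, the number in each, and whether one was sham. Correct the sham and two-group wording to match.
2. Replace the two-group rule with one baseline-adjusted repeated-measures model for the continuous scales. Include all randomised participants, one condition level per randomised arm, and condition-by-visit terms. A participant random intercept and Kenward-Roger degrees of freedom would suit this sample size. Use the same grouping and contrast for hospitalizations and for any non-parametric fallback.
3. Name one primary contrast, outcome and visit; all other contrasts are secondary. The outcome lists must be reconciled first: the synopsis has "Primary Outcomes: Young Mania Rating Scale (YMRS); Altman Self-Rated Mania Scale (ASRM); Average Hospitalizations", whereas Primary Endpoint has PANSS in place of YMRS. If a sham exists, say whether personalized tACS (the Rationale's question) or pooled active tES (the Primary Objective) is compared with it. If not, personalized tACS against cathodal tDCS is the option best supported by the Rationale, for the sponsor to confirm.
4. If no sham was randomised, limit the primary objective and conclusion to relative effects among active conditions plus feasibility, and report before-after change as uncontrolled.
5. The Design text is in the past tense. State whether outcome data had been seen when the contrast was named and, if so, label it post hoc.

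**Cost.** No new data or participants are needed. The claim narrows if there was no sham, the contrast may have to be called post hoc, and one level per arm leaves only about 10 or 9 between-participant degrees of freedom after baseline adjustment.
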